## 17.8. Record Retention

The sponsor and investigator will retain all records and documents pertaining to this study. They will be available for inspection by the appropriate regulatory agencies. In addition, the Investigator will retain the source documents from which the information entered on the eCRF was derived. These records are to be retained in a secure storage facility maintained by the investigational center until 2 years after approval of the above-listed study devices or termination of the study, whichever is longer. The Investigator should not dispose of these records without the approval of the sponsor.

## 17.9. Suspension or Early Termination of Clinical Study

Sponsor or a Regulatory Authority may decide to suspend or prematurely terminate the clinical study (e.g. if information becomes available that the risk to study subject is higher than initially indicated, lack of enrollment, if interim analysis indicates that the results significantly differ from expectations relative to study objectives or statistical endpoints, or because of a business decision). If the clinical study is terminated prematurely or suspended, sponsor shall promptly inform the investigators of the termination or suspension and the reason(s) for this. The investigator shall then promptly inform the reviewing IRB and the study subjects.

## 17.9.1. Early Investigational Center Suspension or Termination

Sponsor, IRB or a Regulatory Authority may decide to suspend or prematurely terminate an Investigational center (e.g. in case of expiring approval of the reviewing IRB, non-compliance to the CIP or lack of enrollment). If an Investigational center is suspended or prematurely terminated, Sponsor shall promptly inform the investigator(s) of the termination or suspension and the reason(s) for this. The investigator shall then promptly inform the reviewing IRB and the study subjects.

When the risks are found to outweigh the potential benefits or when there is conclusive proof of definite outcomes, investigators must assess whether to continue, modify or immediately stop the clinical study in the respective Investigational center and immediately inform the sponsor and IRB, if applicable.

## 17.9.2. Subject Follow-Up In Case of Termination

In case of early investigational center suspension or termination, all subjects should be contacted to plan an early Termination visit at the Investigational Center. All efforts will be made to complete and report all study observations at the time of termination. The subject will return the study devices to the Investigational Center.

## 17.10. Study Close Out

Upon completion of the study, when all subjects have completed the follow-up visits, all eCRFs have been entered and all related queries have been resolved, the sponsor and/or its designees will notify the investigational center of its intention to close out the study and a close-out visit will be performed. All study devices and all unused study materials will be accounted for through reconciliation with shipment logs and returned to the sponsor. The Monitor will ensure that the Investigator's regulatory files are up-to-date and complete and that any outstanding issues from previous visits have been resolved. Other issues that will be reviewed at this visit include discussing retention of study files, possibility of investigational center audits, and notifying the IRB of study closure.

## 17.11. Publication and Use of Information

This clinical study will be registered in a public clinical trials registry, ClinicalTrials.gov. Study information and study results will be posted. Furthermore, Medtronic may publish the results of the clinical study in a press release, abstract, scientific journal article, or public presentation.

The contents of this CIP, documentation and results pertaining to this study are confidential and may not be published or disclosed without the written consent of Medtronic. However, participating investigational center(s) will have the right to publish, publicly disclose, present or discuss the results of information pertaining to the study once Medtronic releases or presents a multicenter publication.

# CIP324 Clinical Investigation Plan

10838519DOC

Version H

Page 165 of 173

Medtronic

The identity of the subjects may not be disclosed, unless required by law, to any persons not immediately involved in the study or the study procedures.

---

***Medtronic Confidential***

This document is electronically controlled

056-F275, vA Clinical Investigation Plan Template

## **19.2. Appendix B: Labeling and IFUs of Devices**

The current labeling and IFU for the study devices will be provided to the investigators under separate cover.

## **19.3. Appendix C: Sample Consent Materials**

Samples of the following consent forms/materials will be provided in a separate cover which includes the California Experimental Subject's Bill of Rights (if applicable), ICF/Accent form, and the HIPAA Authorization.

## **20. Version History**

Version	Summary of Changes	Author(s)/Title
A	Not Applicable, New Document.	[REDACTED]

B	

○ Updated Version and date of CIP

○ Updated Table of Content and Glossary

○ Increased number of enrolled subjects and separated age groups of 2-6 years, 7-13 years, and 14-80 years old further into subgroups

○ Updated FST Timing schedule for all age groups

○ FST schedule in 14-80 years of age updated to four 8-hour session.

○ Removed minimum number of subjects needed for each FST group.

○ Updated minimum for diabetes cohorts for insulin requiring subjects

○ Additional sensor wear location (arm/buttock) added to the 2-6 year old subjects to ensure adequate data can be collected for each insertion site. Based on this change, minimum number of subjects and the compression procedures is updated.

○ Updated Procedures Including YSI* FST Timing and SMBG Requirements

○ Updated study period sensor wear repeat rule section

○ Updated repeat rules for in-clinic procedures

○ Updated protocol and challenge guidelines on starting rules with respect to a subject's glucose level, to allow subjects to start the FST session between 60 mg/dL-300 mg/dL (updated from 50 mg/dL to 500 mg/dL).

○ Updated Hyperglycemic Challenge Guidelines to state that glucose time for glucose >300 mg/dL will be limited to

	
---	--	--

[figure not shown]
# CIP324 Clinical Investigation Plan

10838519DOC

Version H

Page 170 of 173

Medtronic

	

○ 60 minutes.

○ Updated Hypoglycemic Challenge Guidelines to state that glucose time for glucose <70 mg/dL will be limited to 2 hours. Additionally, we have stated that subjects should spend no more than 30 minutes between 50-60 mg/dL and require treatment for glucose below 50 mg/dL.

○ Reduced maximum blood draw volume for 2-6-year olds to 1ml/kg during the study.

○ Updated Stopping Rules for Entire Study

○ Added DMC section who will be overseeing interim analysis

○ Updated statement that commercially available devices used outside their approved intended use include subjects 2-to 13 years

○ Updated Sample Size and Power

○ Removed duplication description of Guardian™ Sensor 3 and Guardian™ Connect Transmitter

	
C	

○ Updated Version and date of CIP

○ Updated Table of Content

○ Updated FST Timing schedule

○ Extended windows for Start of study period to 60 days from Visit 4 to end of study under Visit Schedule for all subjects.

○ Removed duplicate entry description under Section 9.2.2.7

○ Updated interim analysis section to perform one of 2 primary effectiveness endpoint within <math>\pm 15</math> mg/dL mean agreement rate when SG less than (<) 70 mg/dL.

○ Updated YSI™*Retention section

	

**Medtronic Confidential**

This document is electronically controlled

056-F275, vA Clinical Investigation Plan Template

# CIP324 Clinical Investigation Plan

10838519DOC

Version H

Page 171 of 173

Medtronic

D	

○ Updated Version and date of CIP

○ Updated Table of Content

○ Updated Study Design and Study Procedures for 14-80 years: Added that the study procedures may be done in a camp/hotel setting, removed hyper/hypo challenges requirements for subjects 14-17 years old and clarified specific study procedures for subjects undergoing challenges.

○ Updated FST Timing schedule

○ Updated site to instruct subjects to wear 176-188 hours of sensor wear

○ Added site to recommend subjects to set alarm (e.g., on their phone) to check their fingersticks (SBMG) at insertion, 2 hours, 10 hours, and 24 hours on Day 1 and also one approximately at the same time every day as time of the insertion.

○ Updated Deviation Handling section

○ Updated Secondary Endpoint for ZEUS Algorithm

○ Updated Pairing Scheme

○ Added Exploratory Analysis

○ Updated Discharge Criteria Guidelines

	
---	---	--

# CIP324 Clinical Investigation Plan

10838519DOC

Version H

Page 172 of 173

Medtronic

E	

○ Updated Version and date of CIP

○ Updated Table of Content

○ Updated additional clarification regarding the hotel/camp study requirements.

○ Added back hyper/hypo challenges requirements for subjects 14-17 years old

○ Updated Treatment Assignment

○ Added back 40-400 mg/dL operating range from the Secondary Analysis

○ Updated Interim Analysis section

○ Updated Discharge Criteria Guidelines back to Version C

	
F	

○ Updated Glossary

○ Updated Primary Endpoint and Guardian™ Sensor (3) accuracy for ZEUS Algorithms

○ Updated Stopping Rules for Entire Study

○ Removed DMC section as CEC will do the adjudication

○ Corrected Investigator Reporting requirements for Final Report

○ Updated Interim Analysis section

○ Updated IRB name and contact chairperson

○ Updated MC2 abbreviation

○ Updated References section

○ Updated Hyperglycemic and Hypoglycemic Challenge Guidelines

	

[figure not shown]
# CIP324 Clinical Investigation Plan

10838519DOC

Version H

Page 173 of 173

Medtronic

G	

○ Updated Glossary

○ Updated statistical testing for Guardian™ Sensor (3) accuracy for ZEUS Algorithms

○ Removed Guardian™ Sensor (3) accuracy when SG less than 70 mg/dL, Threshold of 75% section (under Sample Size and Power)

○ Updated Interim Analysis section

○ Updated References section

	
H	

○ Updated Interim Analysis section

	

---

**Medtronic Confidential**

This document is electronically controlled

056-F275, vA Clinical Investigation Plan Template

Current methods of continuous glucose monitoring (CGM) include the use of subcutaneous (SQ) glucose sensors worn by the user, which convert glucose from the subject's interstitial fluid into an electronic signal, the strength of which is proportional to the amount of glucose present in the fluid. A CGM sensor is typically attached to a transmitter, which sends interstitial glucose information to a monitor (e.g. the Guardian™ Connect App) as radio frequency (RF) signals. The sensor is composed of a microelectrode with a thin coating of glucose oxidase beneath several layers of biocompatible membrane. The monitor is the data collection/user interface of the system and provides continuous real-time glucose values to the user, as well as the option to set high/low glucose alerts according to the individual patient's needs.

The Medtronic MiniMed™, Inc. (d/b/a "Medtronic Diabetes") family of Continuous Glucose Monitoring Systems (CGMS) measures SQ glucose continuously over various ranges of time. The newest generation Medtronic MiniMed™ SQ Glucose Sensor (Guardian™ Sensor 3) was approved by the United States Food and Drug Administration (FDA) for commercialization as part of the MiniMed™ 670G System in September 2016. The Medtronic MiniMed Glucose Sensor is a glucose sensor designed to work in Medtronic CGM systems to help users manage their diabetes.

Medtronic has developed a new advanced sensor calibration algorithm, called the "Zeus" algorithm, for use with Guardian™ Sensor (3). The "Zeus" algorithm is intended to minimize or eliminate required calibrations, which will reduce user burden. This algorithm will be implemented into a new Transmitter based on the Guardian™ Connect transmitter.

In this study, sensor data from Guardian™ Sensor (3) will be collected in a blinded approach, where commercial Guardian™ Connect Transmitters will be used as a recorder for the purposes of data collection. There will not be any live data communication during the study as no mobile application will be used. At the end of the study, raw sensor data collected by the Guardian™ Connect Transmitters will be processed using the Zeus algorithm and various calibration schemes.

Testing on human subjects is necessary to characterize the accuracy of this sensor algorithm. For purposes of this study, subjects will wear the study devices with Guardian™ Sensor (3). Subjects will manage their diabetes independent of the Guardian™ Sensor (3) values. During YSI™*/SMBG FST, venous blood glucose concentrations or SMBG (subjects 2-6 years only) will be measured periodically; these values will be compared to sensor glucose values (SGVs) in order to determine sensor accuracy.

Accuracy data will be calculated based on comparing calibrated glucose sensor values to a "gold standard" (Yellow Springs Instrument [YSI™*] plasma glucose values) in subjects during YSI™* frequent sample testing (FST). The YSI™* glucose analyzer, Model 2300, has been the recognized standard for the measurement of blood glucose and will be utilized across the investigational centers for the tests.

4. Study Objectives

The primary objective of the study is to demonstrate the accuracy of Guardian™ Sensor (3) when used over a period of 7 days (i.e., 170 hours) with the system in subjects 2-80 years of age.

5. Investigation Plan

The study is a multi-center, randomly assigned, prospective, single-sample correlational design without controls. Subjects will be randomly assigned to sensor location, FST day, and FST time.

A total of up to 460 previously-diagnosed type 1 and 2 diabetes subjects will be enrolled in order to have 244 subjects (122 adults and 122 pediatrics) complete study.

- Cohort1 (Adults): N= 122 subjects 18-80 years old
 - N= 15 minimum subjects age 18-29 years old
 - N= 15 minimum subjects age 30-60 years old
 - N= 15 minimum subjects age 61-80 years old
- Cohort2 (Pediatrics): N= 122 subjects 2-17 years old
 - N= 15 minimum subjects 2-4 years old
 - N= 15 minimum subjects 5-6 years old
 - N= 20 minimum subjects 7-10 years old
 - N= 20 minimum subjects 11-13 years old
 - N= 24 minimum subjects 14-17 years old

6. Determination of Sample Size

6.1 Guardian™ Sensor (3) accuracy, Threshold of 75%

The sample size selected is based on the primary effectiveness endpoint, which is the within 20% mean agreement rate (± 20 mg/dL when Reference BG less than ($<$) 80 mg/dL) in comparative readings of paired Guardian™ Sensor (3) and YSI™* glucose readings in FST days. On those 4 FST days, 8 hours of paired testing will be recorded.

Data from CIP318 and ERP2018-11254 study was used for power estimation via simulation.

The simulation was performed 1000 times and the 95% lower confidence limit of 75%. The results of the simulation indicated that a sample size of 122 will yield greater than 80% power.

7. Statistical Methods

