## 15.5. Sample Size and Power

### 15.5.1. Guardian™ Sensor (3) accuracy, Threshold of 75%

The sample size selected is based on the primary effectiveness endpoint, which is the within 20% mean agreement rate ( $\pm 20$  mg/dL when Reference BG less than ( $<$ ) 80 mg/dL) in comparative readings of paired Guardian™ Sensor (3) and YSI™\* glucose readings in FST days. On those 4 days, 8 hours of paired testing will be recorded.

Data from CIP318 and ERP2018-11254 study was used for power estimation via simulation.

The simulation was performed 1000 times and the 95% lower confidence limit of 75%. The results of the simulation indicated that a sample size of 122 will yield greater than 80% power.

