## 15.7. Assignment to Day of YSI™\* FST

Adult subjects and subjects with age of 14 - 80 will be required to attend four 8-hour sessions of frequent sampling in which agreement between YSI™\* and Guardian™ Sensor (3)s connected to the Guardian™ Connect Transmitters will be evaluated.

Pediatric subjects with age of 7 – 13 will be required to attend two 6-hour sessions of frequent sampling in which agreement between YSI™\* and Guardian™ Sensor (3)s connected to the Guardian™ Connect Transmitters will be evaluated.

Pediatric subjects with age of 2 – 6 will be required to attend two 4-hour sessions of frequent sampling in which agreement between SMBG and Guardian™ Sensor (3)s connected to the Guardian™ Connect Transmitters will be evaluated.

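### The only stated basis for N=122 and more than 80% power, four 8-hour YSI days, is not the schedule of children aged 7-13, so the figure is unsupported for the eight pediatric primary tests

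*SAP*

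**What the plan says.** The sample-size text is almost identical in SAP 6.1 and Protocol 15.5.1. It defines the endpoint on sensor-YSI pairs, names two earlier studies as the data source, and gives one sampling schedule: "On those 4 FST days, 8 hours of paired testing will be recorded" in the SAP and "On those 4 days, 8 hours of paired testing will be recorded" in the protocol. Its conclusion is "The results of the simulation indicated that a sample size of 122 will yield greater than 80% power". The true agreement rate, the variance, the within-subject correlation and the ages simulated are not given.

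SAP section 5 applies the same number to each cohort, aiming for "244 subjects (122 adults and 122 pediatrics) complete study", and defines the second cohort as "Cohort2 (Pediatrics): N= 122 subjects 2-17 years old".

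The sampling schedules are in Protocol 15.7:
- Ages 14-80: "Adult subjects and subjects with age of 14 - 80 will be required to attend four 8-hour sessions of frequent sampling".
- Ages 7-13: these children "will be required to attend two 6-hour sessions of frequent sampling", with YSI as reference.
- Ages 2-6: two 4-hour sessions with fingerstick (SMBG) reference only.

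SAP 7.9.1 lists 16 primary tests. Eight are pediatric: buttock and arm, each with four calibration schemes. Each is a one-sided GEE test of the mean agreement rate with YSI against 75%. SAP 7.8 sets the final threshold at 0.041.

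**The concern.** The one power figure in the plan is attached to a data structure that a large part of the pediatric cohort will not have. Fewer sessions make each child's agreement rate less precise. Mixing children with four sessions and children with two also makes the clusters unequal. If the GEE weights by readings, it leans on the 14-17 year olds and lowers the effective number of subjects.

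Half of the primary tests are affected. If a pediatric block fails, a reader who trusts the printed figure could take it as evidence against the sensor in a well-powered test. The sponsor also plans separate pediatric interim looks to guide enrolment (SAP 7.8), and should know what those tests can detect. Type I error, the estimates and the confidence limits are not affected.

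**Working it through.** **1. The plan's own figure.** It cannot be reproduced, because the true rate and the variance are not stated. With a normal approximation, one-sided alpha 0.05 and N=122, 80% power needs (true rate − 75)/SD = (1.645 + 0.842)/√122 = 0.225. For an assumed between-subject SD of 10, 15, 20 or 25 points, that is a true rate of about 77.3%, 78.4%, 79.5% or 80.6%. The figure can be neither confirmed nor refuted.

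**2. Schedule against stated basis.**

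| Age | Sessions | YSI hours | Readings at 15-minute spacing |
|---|---|---|---|
| Stated basis | 4 × 8 h | 32 | 128 |
| 14-17 | 4 × 8 h | 32 | 128 |
| 7-13 | 2 × 6 h | 12 | 48 |
| 2-6 | 2 × 4 h, SMBG | 0 | 0 |

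Ages 7-13 supply 12/32 = 37.5% of the stated YSI hours. The 15-minute spacing is from Protocol 10.5.1, which samples more often below 75 mg/dL.

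**3. Age mixes the minimums allow (SAP section 5).** The pediatric minimums are 15 + 15 (ages 2-6), 20 + 20 (ages 7-13) and 24 (ages 14-17). They sum to 94 of 122, so 28 places are free.
- Ages 14-17: at least 24 and at most 122 − 30 − 40 = 52, which is 20% to 43% of 122.
- Ages 7-13: at least 40. With ages 2-6 at 30, at most 122 − 30 − 24 = 68. That makes them 40/92 = 43% to 68/92 = 74% of the children aged 7-17.
- Children who can supply sensor-YSI pairs: at most 122 − 30 = 92, and at fewest 40 + 24 = 64.

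**4. Illustration of the session effect alone.** Assumptions:
- All 122 children are counted as having YSI, to isolate this point.
- True rate and variance components are the same as in the four-session design.
- Sensor variance is 1 and session variance is r, with r from 0.5 to 4 assumed.
- The shorter session length is ignored.

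Per-subject variance is v₄ = 1 + r/4 with four sessions and v₂ = 1 + r/2 with two. The variance of the pooled mean is Σn·w²·v/(Σn·w)², with weights w equal or proportional to readings (48 and 128). Power = Φ(2.486·√[(v₄/122)/Var] − 1.645) when the base is exactly 80%.

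Example: r = 1, 43% aged 7-13, equal weights. The 122 split into 53.0 and 69.0. Var = (53.0 × 1.5 + 69.0 × 1.25)/122² = 0.01114, against 1.25/122 = 0.01025. Then 2.486 × √(0.01025/0.01114) = 2.384, and Φ(2.384 − 1.645) = 77%.

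| Aged 7-13 | Weights | r=0.5 | r=1 | r=2 | r=4 |
|---|---|---|---|---|---|
| 43% | equal | 78.3% | 77.0% | 75.1% | 72.9% |
| 43% | readings | 73.6% | 73.3% | 72.8% | 72.2% |
| 74% | equal | 77.2% | 75.0% | 72.0% | 68.4% |
| 74% | readings | 70.4% | 69.5% | 68.1% | 66.5% |

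The overall range is about 67-78%. From a base of 85% it is 72-84%, from 90% it is 79-89%, and from 95% it is 86-94%. With r = 0 and equal weights there is no loss.

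**5. Cross-check with another model.** Put all 122 on two 6-hour sessions with intra-subject correlation ρ from 0.02 to 0.30, and per-subject variance proportional to (1 + (m − 1)ρ)/m for m readings. At ρ = 0.1 the ratio of four-session to two-session variance is (13.7/128)/(5.7/48) = 0.901, so power is Φ(2.486 × √0.901 − 1.645) = 76%. Over the range of ρ, power is 66-79% from a base of 80% and 78-89% from a base of 90%. Direction and rough size agree.

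**The case against.** The strongest reply is that the disputed sentence says what will be recorded in this study. It does not say what was simulated. The simulation drew on two earlier studies that the reader cannot see, and it may have used pediatric data on the pediatric schedule. That stands: a reader might infer that the simulation was run on adult sessions only, and the documents do not establish this. But the sentence is still wrong as a description of the pediatric blocks, and neither document gives another basis for them.

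A reader might also infer that pediatric power is below 80%. The documents do not support that either.
- The plan says more than 80%, not exactly 80%. From a base of 90%, every equal-weight setting stays at 80% or above, and only the most extreme reading-weighted setting falls below (78.6%).
- The larger losses need weighting by readings, as under an independence structure. That is one of three structures QIC may select. An exchangeable fit with non-trivial correlation moves toward equal weights and smaller losses.
- Under Protocol 9.1, ages 2-13 do not undergo glucose challenges. Their agreement rate and session variance may differ from those of older subjects in either direction, and power depends mainly on the distance above 75%.

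A third objection is that step 4 models 122 children with YSI when at least 30 have SMBG only. This is correct. Step 4 isolates the session effect and is not the power of any real pediatric test. The SMBG-only reference at ages 2-6 is a separate matter and may cost more, but the session mismatch would remain if it were resolved.

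**Conclusion.** The point holds as a fault in the stated basis. Four 8-hour YSI days describe at most 52 of the 122 children, while at least 40 have 12 YSI hours instead of 32. The only power figure in the plan is therefore unsupported for eight of the 16 primary tests. This follows from the documents alone and needs no assumption about variance.

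The size of any loss is not established. The 67-78% and 79-89% ranges rest on an assumed base power, assumed variance ratios, a common true rate and 122 children with YSI. They show that the session difference can matter. They do not show that pediatric power is below 80%. The correction is worth making because it concerns half the primary tests and costs little.

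**What to change.** In SAP 6.1 and Protocol 15.5.1, limit the four-day, 8-hour wording and the power statement at N=122 to the adult blocks. If the sponsor confirms that the simulation used the pediatric schedule, correct the sentence to say so instead.

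Rerun the existing simulation for the pediatric blocks, with:
- two 6-hour sessions for ages 7-13 and four 8-hour sessions for ages 14-17;
- the range of age mixes the minimums allow, since the plan fixes no single mix;
- only children who supply sensor-YSI pairs (64 to 92 if ages 2-6 remain SMBG-only);
- the planned GEE and the final threshold of 0.041, where the present text cites a 95% limit.

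Print the resulting pediatric power, or the true agreement rate detectable with 80% power, together with the simulation inputs. Do this in the same rerun as any correction to the reference for ages 2-6.

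The cost is one rerun and a few sentences in each document. Enrolment, visits and procedures do not change. The downside is that the stated pediatric power may be less favourable.
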